Exclusion Criteria:	
Patients with:
 
 1. Contraindications for moderate exercise 2. Implanted devices (e.g., pacemakers) that may interact with Tanita scale 3. Previous coronary or cerebrovascular event within 6 months of screening or active or clinically significant coronary and/or peripheral vascular disease 4. Low hematocrit (< 28 UNITS). 5. Pre-existing liver disease and/or ALT and AST $>2.5 \times$ UNL 6. Kidney disease at levels defined by: serum creatinine levels ≥ 1.5 mg/dL for men, ≥ 1.4 mg/dL for women, estimated CrCl ≤ 50 mL/min 7. History of pancreatitis, or cancer (except basal cell carcinoma) 8. Statin use started (or dose change) in the last 3 months, 9. Use of oral or injectable anti-diabetic medication other than Metformin 10. Daily use of a consistent long-term steroid medication (oral, inhaled, injected) within the last 3 months 11. Systolic BP > 140 mmHg and Diastolic BP > 90 mmHg at screening visit. 12. Active wounds or recent surgery within 3 months. 13. Inflammatory disease, or chronic current use of anti-inflammatory drugs within the last 3 months. 14. triglycerides >400 mg/dL 15. untreated hyper/hypothyroidism 
Additionally, patients who are active smokers, patients who are pregnant, nursing women, and post-menopausal women who are on hormone replacement therapy will be excluded.
 
Patients on low dose oral contraceptives will be allowed to participate as these formulations contain lesser amount of estrogens.

----------------------------	---

Criteria for Evaluation: (Efficacy, safety, stopping rules, etc.)	Subjects will be screened at week -4, then evaluated for end points at weeks 0, 6 and 12. Study participation will be stopped for adverse effects at the discretion of the study investigator. Subjects may stop study participation at any time and for any reason.
Statistics:	The total sample size requested, accounting for attrition over the 12-week period, is 20 subjects per group or 40 subjects total. Sample size estimates were based on the effects of exercise on CD34+/KDR+ cells as described in the literature. The effect of a single session, as well as extended training, on healthy subjects or those with existing cardiovascular conditions appears to increase the CD34+/KDR+ cells. This will provide 73% power (see statistics section). A p-value of less than 0.05 will be considered statistically significant.

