8 STATISTICAL CONSIDERATIONS

Statistical Analysis:

Sample Size Estimation:

The total sample size requested, accounting for attrition over the 12-week period, is 21 subjects per group or 42 subjects total.

Sample size estimates were based on the effects of exercise on CD34+/KDR+ cells and VEGF, as described in the literature⁴⁷⁻⁵⁰. The effect of a single session, as well as extended training, on healthy subjects or those with existing cardiovascular conditions appears to increase the CD34+/KDR+ cells and VEGF.

To compute sample size we used the approach suggested by Diggle, Liang, & Zeger (1994)⁵¹ which compares the rates of change in the two study groups over time. This approach incorporates the number and interval of time points and the correlation among repeated measures. For this study, we will employ one baseline and two follow-up measures at 6 and 12 weeks. Further, we will assume a correlation 0.60 among repeated measures of the outcome. [We consider this a conservative estimate since Frison and Pocock (1992)⁵² suggest a correlation of 0.65 as reasonable in the absence of an existing estimate. We also note that as this correlation increases, statistical power also increases.

The results in the table below show the expected mean difference in study groups at the end of follow-up, as well as the average rate of change in the two groups at 80% power and 90% power. To estimate the effect of saxagliptin on the CD34+/KDR+ cells, we expect that the effect would be at least 25% greater than the effect seen for exercise alone. Using the results from Sandri et al. (2005)⁴⁹ for the rate of change and the variability, the CD34+/KDR+ cells increased an average rate of about 4/wk with a standard deviation of about 15. Thus, for a 25% increase in the rate of change for the CD34+/KDR+ cells due to saxagliptin, a sample size of 18 subjects per group would provide about 84% power, assuming measures taken at baseline and 2 equally-spaced time points over 12 weeks. At the conclusion of follow-up, we would expect study groups to differ by an average of 12 cells. If the effect of saxagliptin is only 20%, a sample of 18 would provide about 70% power, whereas a sample of 20 would provide about 73% power.

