For VEGF, the results from Sandri et al. (2005)⁴⁹ were mixed with one study group showing a .6 pg/mL per week increase and another showing a 0.5 pg/mL per week decrease after 4 weeks of training. If we assume that saxagliptin will increase VEGF consistently at 0.3 pg/mL per week difference in slopes compared with exercise alone, then assuming a standard deviation of 5 and correlation of 0.60 among repeated measures, a sample size of 18 per group would provide about 77% power to detect a difference in slopes of 0.3 pg/mL per week or a mean difference in the groups at the end

of the study of 3.6 pg/mL. A sample size of 27 would provide about 90% power to detect the same effects.

Thus, we feel that a sample size of at least 18 subjects per group with complete data would provide sufficient power for the study outcomes. In order to insure that we will have 18 per group who complete the study, we will enroll 20 subjects per group in order to account for attrition over the 12-week period.

Biochemical Measure	Mean difference at end of 12 weeks	Sample Size per group	Power
CD34+/KDR+ cells	12 cells (25% increase; 4/wk vs. 5/wk)	18	0.84
		22	0.90
VEGF, pg/mL	3.6 pg/mL (50% increase; (0.6/wk vs. 0.9/wk)	18	0.77
		27	0.90

Data Analysis.

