The distributional assumptions of all measures will be examined. Means and standard deviations will be computed for continuous measures and proportions for categorical variables. Graphical representations of the mean group slopes and individual slopes will be generated and inspected. Study groups will be compared to determine whether any imbalance between the groups on patient characteristics remain after randomization. If imbalance is evident, by inspection, all models will be adjusted for the unbalanced covariates. Change in outcome over time will be examined using a multilevel approach with linear mixed models (LMM)^{53,54}. The longitudinal multilevel modeling approach will enable us to examine characteristics of within-person change, as well as between-group differences that may influence change. LMMs handle missing data more efficiently than traditional ANOVA designs. In the linear mixed models, the patient is considered a random effect and the outcome measured at specific time points is nested within patient. In an initial model containing only the variable TIME, we will use a likelihood ratio test to determine whether a random effect for time should be modeled. The model below represents a random intercept for patient and a random coefficient for TIME.

$$Y_{ij} = \beta_0 + \beta_1 Time_{ij} + u_{i0} + u_{i1} Time_{ij} + \varepsilon_{ij}$$

We will examine whether TIME may be modeled linearly by testing the added contribution of TIME (represented with two indicator variables) to a model with TIME as a single continuous variable. Assuming time may be modeled as a continuous variable, subsequent analyses will add study group and other patient characteristics as covariates. We are particularly interested in whether there is a significant interaction between study group and time, adjusting for other patient level covariates. A significant interaction would indicate that the slopes in outcome over time differ by study group. If the global test of interaction is significant, subsequent significance testing of the pair wise comparisons of group slopes group will be adjusted for multiple comparisons. The model also includes coefficients for the group-by-time interactions and random effects for patient and time.

$$Y_{ij} = \beta_0 + \beta_1 Time_{ij} + \beta_2 Group_i + \beta_3 (Time_{ij} \times Group_i) + u_{i0} + u_{i1} Time_{ij} + \varepsilon_{ij}$$

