In the event that TIME is modeled using indicator variables, two indicator variables will be used to represent the three time points, with baseline serving as the reference category. The interaction between GROUP and TIME will be modeled in a similar fashion using two additional indicator variables. The above multivariable model enables us to adjust for time-varying covariates, such as glucose. Since glucose will be measured contemporaneously with the outcomes at each visit, however, causal interpretations of glucose and any outcome are suspect. As such, we will consider glucose as a nuisance covariate, and consider any relationship between glucose and an outcome as merely associative.

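### Two pre-tests decide the covariance model and whether the group-by-time test has 1 or 2 degrees of freedom, so the treatment test is not fixed and only one branch is powered

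*Combined protocol and SAP*

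**What the plan says.** The Data Analysis part of Section 8 starts from a model with time only, in which "we will use a likelihood ratio test to determine whether a random effect for time should be modeled". No significance level is given for that test.

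The next step concerns the shape of time: "We will examine whether TIME may be modeled linearly by testing the added contribution of TIME" as two indicators to a model with a single continuous time variable. Again no level is given. Group enters only in later models, so as the steps are ordered both pre-tests are run without group.

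If time passes as linear, the treatment test is the single time-by-group coefficient, a difference in slopes. If not, the plan switches: "In the event that TIME is modeled using indicator variables, two indicator variables will be used to represent the three time points", and the interaction is coded with two further indicators. No single contrast, such as the week-12 difference, is named as primary in that case.

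The Sample Size Estimation part of Section 8 powers a comparison of rates of change only. The printed final model includes a random time effect, but the text does not say that this overrides the likelihood ratio test.

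**The concern.** The confirmatory test should be known before the data are seen. Here its standard error depends on one pre-test and its degrees of freedom and estimand on another. One branch tests a slope difference; the other tests jointly whether the arms differ in change at week 6 or week 12. As written, the steps would be repeated for each outcome, so cell counts, functional assays and gene expression could each end with a different test.

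Two things are at stake. The first is power: the 2-df test spends a degree of freedom on curvature in the treatment effect, and the sample size was not set for it. The second is validity: if patients' slopes truly vary and the likelihood ratio test drops the random slope, the slope standard error is too small. With 36 completers and three visits that pre-test has limited power.

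**Working it through.** **Inputs.** All are from Section 8 except the significance level, which is in the synopsis.
- Visits: "we will employ one baseline and two follow-up measures at 6 and 12 weeks". Times 0, 6, 12 have squared deviations from their mean of 36 + 0 + 36 = 72.
- Correlation: "we will assume a correlation 0.60 among repeated measures of the outcome".
- Variability: CD34+/KDR+ cells "increased an average rate of about 4/wk with a standard deviation of about 15". Residual variance is 15² × (1 − 0.60) = 90.
- Effect: slopes of 4 and 5 cells per week, a difference of 1 per week or 12 cells at week 12.
- Completers: 18 per group.
- Level: "A p-value of less than 0.05 will be considered statistically significant"; sidedness is not stated.

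**Reproducing the plan's figure.** SE of the slope difference = √(2 × 90 / (18 × 72)) = √0.1389 = 0.3727, so d/SE = 1/0.3727 = 2.683.
- One-sided 0.05: Φ(2.683 − 1.645) = 85.0%, against the stated 84%.
- Two-sided 0.05: Φ(2.683 − 1.960) = 76.5%.

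The stated power is therefore for the 1-df slope test and matches a one-sided level. Sidedness is a separate matter; both branches are compared below at 0.05, two-sided for the 1-df test.

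**1 df against 2 df.** For a linear treatment effect both tests have noncentrality 2.683² = 7.2. The 2-df power comes from a noncentral chi-square distribution.

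| Outcome, effect, n per group | 1 df | 2 df | Loss (points) |
|---|---|---|---|
| CD34+/KDR+, 25%, 18 | 76.5% | 66.9% | 9.7 |
| CD34+/KDR+, 25%, 20 | 80.7% | 71.8% | 9.0 |
| CD34+/KDR+, 20%, 18 | 57.4% | 47.0% | 10.4 |
| VEGF, 0.3 pg/mL per week, 18 | 67.5% | 57.1% | 10.4 |

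Losses are taken from unrounded powers.

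**How often the 2-df branch is chosen.** The linearity test responds to curvature common to both arms, whatever the shape of the treatment difference. With 36 patients the mean of the curvature contrast (week 0 − 2 × week 6 + week 12)/√6 has SE √(90/36) = 1.58. I take a pre-test level of 0.05, since the plan gives none.
- Linear common trend (0, 24, 48 cells): chosen about 4–5% of the time, essentially the pre-test level.
- Mildly curved (0, 30, 48; assumed): contrast −12/√6 = −4.90, ratio 3.10, chosen with probability Φ(3.10 − 1.96) ≈ 87%.
- Clearly curved (0, 36, 48; assumed): contrast −24/√6 = −9.80, ratio 6.2, chosen in practically every trial.

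**Whole procedure, simulated** (40,000 trials per setting, 18 per group, linear 12-cell effect):
- Linear common trend: 74.6% power, against 75.6% for a fixed 1-df random-intercept test.
- Clearly curved common trend (0, 36, 48): 64.5%, against 74.2% for a fixed 1-df random-slope test.

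**Type I error, same simulation.** The slope SDs are assumptions; the plan gives none. At a slope SD of 0.75 per week the likelihood ratio test keeps the random slope in only 31.9% of trials, and the whole procedure rejects 6.0% of the time under the null. Over slope SDs from 0 to 1.5 per week with a linear trend, and for the curved trend without slope variation, the range is 4.8–6.0%.

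**Week-12 contrast.** With complete data at 0, 6 and 12 weeks, the least-squares slope is exactly (week 12 − week 0)/12. The week-12 change contrast then has the same noncentrality, 7.2, and the same 76.5% large-sample power, without assuming linearity.

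**The case against.** The strongest reply is that the plan's planning model is linear in both arms ("12 cells (25% increase; 4/wk vs. 5/wk"), so on its own terms the 2-df branch is rarely reached and costs about 1 point. That stands. The 10-point figure is conditional on that branch being chosen and the treatment difference being linear. A reader might infer that the trial simply loses 10 points; the documents do not support that. They do not exclude it either: all patients start a lifestyle programme four weeks before baseline and continue it, and a response that levels off by week 12 would be exactly the shared curvature that triggers the switch.

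A reader might also infer type I error of 7–10%. That range belongs to a random-intercept model used alone at slope SDs of 0.75–1.5 per week, which is not the plan's procedure because the likelihood ratio test comes first. Those slope SDs also depart from the planning inputs. Added to residual variance 90 and intercept variance 135, an SD of 0.75 gives a week-12 variance of 225 + 144 × 0.5625 = 306 (SD 17.5) and a week 0–12 correlation of 135/√(225 × 306) = 0.51, not 0.60.

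Nor are the pre-tests worthless. If the effect is complete by week 6 (0, 12, 12), the 2-df noncentrality is (72 + 24)/10 = 9.6, giving 79.8% power against 76.5% for 1 df. For a transient effect (0, 12, 0) the 2-df test also has 79.8%, while a week-12 contrast has only 5%.

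Finally, the selection rule is written in advance and, as ordered, does not look at group. This is not free choice guided by the treatment estimate. What remains is that the rule has no stated levels, leads to two different treatment hypotheses, and is powered for one of them.

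**Conclusion.** The concern holds as a worthwhile, inexpensive improvement. The treatment test and estimand are not fixed, the 2-df branch has no named primary contrast, and power is stated for the slope branch only.

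The cost in power for the 12-cell effect ranges from about 1 point (linear common trend) to nearly 10 points (clearly curved common trend with a linear treatment difference). These figures rest on SD 15, correlation 0.60, 18 completers per group, two-sided 0.05 and an assumed pre-test level of 0.05; the curved trends are also assumed.

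Type I inflation is small, at most about 6% under the assumed slope SDs, and is not the main reason to change. The gap between the stated 84% and 76.5% is due to sidedness and should not be added to this point.

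**What to change.** Drop both pre-tests. For every outcome pre-specify one mixed model with time as categorical (weeks 0, 6, 12), group, group-by-time, unstructured within-patient covariance and Kenward-Roger degrees of freedom. Name the group difference in change from week 0 to week 12 as the single 1-df primary test, with week 6 supportive, and restate power for that test with its sidedness. This matches the plan's own target of a 12-cell difference at the end of follow-up.

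The cost is wording, plus three statistical downsides:
- Unstructured covariance has six parameters against two for a random-intercept model, so up to four more.
- Fewer error degrees of freedom (about 34 rather than 70) cost about 1 point of power: 74.1% against 75.4% in the F-test version for the 25% effect at 18 per group.
- Power is lower than with the 2-df test if the effect is complete by week 6 or is transient. If the investigators consider such a pattern likely, they should say so now and name the contrast that targets it.

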²⁰where Sitagliptin was compared to placebo with endothelial progenitor cells as a outcome measure in patients with type 2 diabetes over 4 weeks. Though our study is over 12 weeks we do not anticipate significant drop in HbA1C in between the two groups in this relatively short time period to act as a confounding factor on CD34+ cell number, function and gene expression. Most clinical studies looking at HbA1C reduction were of a much longer duration of 6 months or above and most DPP-4 inhibitor studies are with animal EPCs where comparison with human CD34+ population is difficult to make. In one study⁵⁸ where saxagliptin was used for 12 weeks in drug-naïve type 2 diabetes patients there was placebo-subtracted HbA1c reduction noted of 0.45-0.63%. It showed mean placebo-subtracted reductions in fasting serum glucose of 20 mg/dL. From our laboratory studies of in vitro human EPC studies we do not think glucose level change of 20 mg/dL is significant enough to account for changes in EPC number, function and gene expression. However we will take this possibility into account during statistical analysis of the results between the saxagliptin and placebo groups.

Lifestyle Intervention for Type 2 diabetes patients²:

To keep uniformity within the cohort regarding lifestyle during the length of the study duration, all patients at entry will ideally receive dietary advice from the research coordinator, a diabetes educator, a registered dietitian (as per American Diabetes Association clinical guidelines²), specifically geared towards type 2 diabetes patients. They will be advised to adhere to 150 minutes of weekly aerobic exercise (50-70% of maximal heart rate) as best as possible. Patient's activity will be monitored using accelerometers and will be downloaded at regular intervals by the research coordinator.

Subjects will be taking 5.0 mg of Onglyza (saxagliptin) or placebo. We choose to use the maximum approved dose of saxagliptin in order to discern a definite effect.

Visits with outcome measurements will be scheduled for morning following overnight 10 hours fast to reduce diurnal variability, and clinical parameters will be obtained at scheduled office visits as depicted in the study schema and will be measured at each outcome visit as follows:

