Week -4: Subjects will be screened and eligibility will be verified based on physical and laboratory tests. We will aim to recruit equal numbers of male and female patients will be recruited. All patients will be educated on the recommended lifestyle changes of maintaining a level of aerobic activity of 150 minutes/ week (non-supervised) and ideally receive dietary advice from the research coordinator, a diabetes educator, or a registered

dietitian (as per American Diabetes Association clinical guidelines²) specifically geared towards type 2 diabetes patients. We plan to monitor activity using accelerometers. We will allow 4 weeks for the patients to reach a steady state while implementing life style (diet and exercise) changes.

Week 0: At this stage patients will be randomized into the study. Subjects will have the first set of measurements. We will make sure that patients still meet the inclusion criteria. They will be started on medication or placebo and will be encouraged to continue 150 minutes/week of moderate physical exercise and dietary management for the remainder of the study.

Weeks 0, 6 and 12: Subjects will all have the same measurements and will continue on study medication or placebo. All primary and secondary measures as outlined before will be carried out.

- Primary Measures: CD34+ cell number, function and gene expression.
- Mononuclear cell population (day 0 of harvest) will be analyzed by FACS to obtain cell counts of different endothelial precursor lineage cells. Combinations of following cell markers will be used, such as CD34, KDR(VEGFR2), CD31, CD144 (VE-Cadherin), CD133 (a progenitor cell marker of indeterminate lineage) and CXCR4 (SDF1 α receptor)^{5,6,8,10,20,21,59}

For:

- CD34/KDR+
- CD34/ CXCR4+
- CXCR4 + CD31
- KDR + CD34
- Some of the MNC population will be put through a human CD34 magnetic bead column using Miltenyi Biotech Column to obtain CD34+ and CD34- cells. The CD34+ cells will be used for
- Colony Forming Unit Assay (CFU Assay) from mononuclear cell population (prior to magnetic bead sorting)
- Migration assay in response to SDF-1 (0, 10, 100 ng/mL) and if sufficient cells are available we will note migration in response to SDF1 (0, 10, 100 ng/mL)

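### The mixed model estimates a free group difference at the pre-dose week-0 visit; on the sizing inputs a common week-0 mean would cut the week-12 contrast variance by about one fifth

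*Combined protocol and SAP*

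**What the plan says.** All analysis text is in section 8, under Data Analysis.

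- The full model adds group to a model in time: "Assuming time may be modeled as a continuous variable, subsequent analyses will add study group and other patient characteristics as covariates". Its equation has an intercept, Time, Group and Time x Group. The text then adds: "The model also includes coefficients for the group-by-time interactions and random effects for patient and time". With time coded from week 0, the Group coefficient is the difference between arms at week 0, and it is unconstrained. The fallback with two indicators for time keeps baseline as the reference and has the same structure.
- The random slope is conditional: "we will use a likelihood ratio test to determine whether a random effect for time should be modeled".
- Other adjustment is foreseen. For visible imbalance: "If imbalance is evident, by inspection, all models will be adjusted for the unbalanced covariates". For glucose: "The above multivariable model enables us to adjust for time-varying covariates, such as glucose". The text after the schedule in section 6.2 says of a possible glucose effect: "However we will take this possibility into account during statistical analysis of the results between the saxagliptin and placebo groups".
- On timing, section 6.2 states: "Week 0: At this stage patients will be randomized into the study. Subjects will have the first set of measurements". Treatment comes afterwards in the same paragraph: "They will be started on medication or placebo and will be encouraged to continue 150 minutes/week".

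Nowhere do the documents set a common week-0 mean or use the week-0 value of the outcome as a covariate.

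**The concern.** Randomisation makes the expected week-0 means equal in the two arms. A model that still estimates a difference there treats chance imbalance as something to be learned. With complete data and no time-varying covariate, the planned interaction test reduces to the unadjusted difference in change from week 0 to week 12. That change score subtracts the whole baseline value, although with a correlation of 0.60 only 60% of a baseline difference is expected to persist.

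With 18 completers planned per arm and 20 or 21 enrolled, precision is scarce. The plan itself puts power at about 70% (18 per group) or 73% (20 per group) if the saxagliptin effect is 20% rather than 25%. The week-0 value that would help is already being collected.

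**Working it through.** **Inputs (section 8, Sample Size Estimation).** SD 15, correlation 0.60 between any two visits, visits at weeks 0, 6 and 12, 18 per group, slope difference 1 cell/week (12 cells at week 12). Significance is at 0.05 (synopsis); sidedness is not stated. The calculation assumes complete data and, at first, no random slope.

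**Step 1. The plan's own power.** For a slope comparison, Var(slope difference) = 2 x SD² x (1 - ρ) / (n x 72), where 72 is the sum of squared deviations of 0, 6 and 12 from their mean. This gives 2 x 225 x 0.4 / (18 x 72) = 0.1389.

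| Case | Stated | One-sided 0.05 | Two-sided 0.05 |
|---|---|---|---|
| CD34+/KDR+, 25%, n=18 | 0.84 | 0.850 | 0.765 |
| CD34+/KDR+, 25%, n=22 | 0.90 | 0.907 | 0.843 |
| CD34+/KDR+, 20%, n=18 | 0.70 | 0.692 | 0.574 |
| CD34+/KDR+, 20%, n=20 | 0.73 | 0.732 | 0.619 |
| VEGF, n=18 | 0.77 | 0.779 | 0.675 |
| VEGF, n=27 | 0.90 | 0.905 | 0.841 |

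The formula reproduces the plan at one-sided 0.05, so both levels are shown below.

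**Step 2. Variance of the week-12 contrast.**

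- Free Group term: 144 x 0.1389 = 20.0 (SE 4.47). Indicator time gives the same value: (2/18) x 225 x 2 x (1 - 0.60) = 20.0.
- Common week-0 mean, indicator time: (2/18) x 225 x (1 - 0.60²) = 16.0 (SE 4.00). The ratio is (1 + ρ)/2 = 0.80, a 20% cut.
- Common week-0 mean, linear time: the ratio is 72 / (180 - 324ρ/(1 + 2ρ)) = 72 / (180 - 88.36) = 0.786. The variance is 15.7, a 21.4% cut.
- Week-0 value as covariate with its coefficient estimated (ANCOVA of week 12): 16.0 x (1 + 1/(2n - 4)) = 16.0 x 33/32 = 16.5, a 17.5% cut.

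A cross-check: the chance week-0 difference has SD 15 x √(2/18) = 5.0 cells. The change score carries 40% of it, with opposite sign, so 2.0 cells. The square, 4.0, is exactly 20.0 - 16.0.

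**Step 3. Power for 12 cells at 18 per group (normal approximation).**

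| Model | Two-sided 0.05 | One-sided 0.05 |
|---|---|---|
| Free Group term | 76.5% | 85.0% |
| Common mean, indicator time | 85.1% | 91.2% |
| Common mean, linear time | 85.7% | 91.7% |

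A t-based simulation (two-sided, 60,000 trials) of change score against ANCOVA gave 74.4% and 82.1%, with type I error 5.0% and 4.8%.

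**Step 4. Sensitivity to the correlation.** The cut with linear / indicator time is 27% / 25% at 0.5, 19% / 17.5% at 0.65, and 16% / 15% at 0.7.

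**Step 5. If a random slope is retained.** The documents give no slope variance or intercept-slope covariance. The following rests on assumed values: intercept variance 135, residual variance 90 (together 225), and a range of slope SDs. Entries are variance cuts with known covariance, linear / indicator time.

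| Intercept-slope correlation | Slope SD 0.25/wk | 0.50/wk | 0.75/wk |
|---|---|---|---|
| -0.4 | 27% / 25% | 31% / 29% | 32% / 30% |
| 0 | 20% / 19% | 18% / 17% | 15% / 14% |
| +0.4 | 15% / 14% | 9% / 8% | 4% / 4% |

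Holding the SD at 15 at both week 0 and week 12, as the plan's single SD implies, forces the covariance to be -6 x (slope variance). At slope SDs of 0.5, 0.75 and 1.0 the correlations are then -0.26, -0.39 and -0.52, and the indicator-time cuts are 24%, 29% and 36%. At the other extreme (slope SD 1.0, correlation +0.5) the known-covariance cut is 0.6%. There the ANCOVA version loses slightly: t-based power 49.5% to 48.3%.

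**Step 6. Do the planned adjustments already capture this?** A covariate fixed over time and entered as a main effect, even the week-0 outcome itself, leaves the complete-data slope contrast unchanged. In one simulated data set, 12 times the interaction coefficient was 8.514 with no covariate, with age, and with the week-0 outcome as main effect. Time-varying glucose moved it to 10.063, but glucose is a different variable and does not supply the baseline outcome.

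**The case against.** The strongest reply is that nothing here is wrong. A random-coefficient model with Group, Time and their interaction is standard, it is pre-specified, its test is unbiased under randomisation, and it estimates the rate-of-change contrast on which the trial was sized. That stands, and it makes this an improvement to precision rather than a correction.

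A second reply is that the one-fifth figure assumes no random slope, while the displayed model has one, subject to a likelihood ratio test. That also stands: the size is firm only on the sizing inputs. Nor do the known-covariance figures charge for estimating the covariance; the 17.5% ANCOVA figure indicates that cost. The simulated powers compare change score with ANCOVA, as stand-ins for the mixed models.

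Three stronger readings are tempting, and the documents support none of them.

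- A reader might infer that the interaction test is biased or the stated power wrong because of the Group term. The stated powers already refer to the unconstrained slope comparison, and baseline noise is inside its standard error.
- A reader might infer that varying slopes usually shrink the gain. Without a slope covariance in the documents, no direction can be claimed, and a constant SD points to a larger gain.
- A reader might infer that the linear slope test has to go. The gain is available under either time coding.

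**Conclusion.** The point holds as an efficiency gain that costs no data. The free week-0 group difference is plain in the model equation, and none of the planned adjustments recovers what it gives up. With complete data, correlation 0.60 and no random slope, the variance cut is 20 to 21%, or 17.5% with an estimated baseline coefficient. That is worth 6 to 9 points of power for the 12-cell target, depending on sidedness and time coding. With a random slope the benefit is uncertain in size: from about nothing when slopes rise strongly with baseline to more than one fifth when the intercept-slope correlation is negative. The change is worth making, but the validity of the trial does not depend on it.

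**What to change.** Before unblinding, specify that both arms share a common week-0 mean: remove the Group main effect and keep the group-by-time term (linear time) or the two group-by-time terms (indicator time), under whichever coding the plan selects. State also whether glucose enters the primary model or only a supportive one.

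An alternative is to model weeks 6 and 12 as outcomes with the week-0 value as a covariate by visit. This could lose about 1 power point in the extreme random-slope case shown above. Replacing the slope test by an indicator-time contrast at week 12 is optional and not needed for the gain.

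Costs: a protocol revision, prepared by the company named in section 9.1.1 and approved by the IRB/IEC. If linear time is kept, the constrained estimate relies slightly more on linearity. With no random slope, its weights on the between-arm differences at weeks 0, 6 and 12 are -0.643, +0.143 and +0.929. A 12-cell effect fully present by week 6 would be estimated as 12 x (0.143 + 0.929) = 12.9, and one appearing only after week 6 as 12 x 0.929 = 11.1. The planned complete-data estimate gives week 6 no weight. The revision should say so.
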